12.1.4.3 Evaluation of Best Overall Response

The best overall response is the best response recorded from the start of the treatment

HCC #:16-054

Version Date: 008/11/2020

until disease progression/recurrence (taking as reference for progressive disease the smallest measurements recorded since the treatment started). The patient's best response assignment will depend on the achievement of both measurement and confirmation criteria.

For Patients with Measurable Disease (i.e., Target Disease)

Target Lesions	Non-Target Lesions	New Lesions	Overall Response	Best Overall Response when Confirmation is Required*
CR	CR	No	CR	≥4 wks. Confirmation
CR	Non-CR/Non-PD	No	PR	≥4 wks. Confirmation
CR	Not evaluated	No	PR	
PR	Non-CR/Non-PD/not evaluated	No	PR	
SD	Non-CR/Non-PD/not evaluated	No	SD	Documented at least once ≥4 wks. from baseline
PD	Any	Yes or No	PD	no prior SD, PR or CR
Any	PD**	Yes or No	PD	
Any	Any	Yes	PD	

* See RECIST 1.1 manuscript for further details on what is evidence of a new lesion. ** In exceptional circumstances, unequivocal progression in non-target lesions may be accepted as disease progression.
 
Note: Patients with a global deterioration of health status requiring discontinuation of treatment without objective evidence of disease progression at that time should be reported as “symptomatic deterioration.” Every effort should be made to document the objective progression even after discontinuation of treatment.
				

For Patients with Non-Measurable Disease (i.e., Non-Target Disease)

Non-Target Lesions	New Lesions	Overall Response
CR	No	CR
Non-CR/non-PD	No	Non-CR/non-PD*
Not all evaluated	No	not evaluated
Unequivocal PD	Yes or No	PD
Any	Yes	PD

* ‘Non-CR/non-PD’ is preferred over ‘stable disease’ for non-target disease since SD is increasingly used as an endpoint for assessment of efficacy in some trials so to assign this category when no lesions can be measured is not advised
		

12.1.5 Duration of Response

Duration of overall response: The duration of overall response is measured from the time measurement criteria are met for CR or PR (whichever is first recorded) until the first date that recurrent or progressive disease is objectively documented (taking as reference for progressive disease the smallest measurements recorded since the treatment started).

The duration of overall CR is measured from the time measurement criteria are first met for CR until the first date that progressive disease is objectively documented.

Duration of stable disease: Stable disease is measured from the start of the treatment until the criteria for progression are met, taking as reference the smallest measurements recorded since the treatment started, including the baseline measurements.

12.1.6 Progression-Free Survival

PFS is defined as the duration of time from start of treatment to time of progression or death, whichever occurs first.

13. DATA REPORTING / REGULATORY REQUIREMENTS

13.1 Data Safety Monitoring Plan

Sponsor/Investigator, Sub-investigators, regulatory, CRS management, clinical research coordinators, clinical research associates, data managers, and clinic staff meet monthly in disease center Data Safety Monitoring Boards (DSMB) to review and discuss study data to include, but not limited to, the following:

- serious adverse events
- subject safety issues
- recruitment issues
- accrual
- protocol deviations
- unanticipated problems
- breaches of confidentiality

Minutes from the DSMB meetings are available to anyone unable to attend the center DSMB.

All toxicities encountered during the study will be evaluated on an ongoing basis according to the NCI Common Toxicity Criteria version 4. All study treatment associated adverse events that are serious, at least possibly related and unexpected will be reported to the IRB. Any modifications necessary to ensure subject safety and decisions to continue, or close the trial to accrual are also discussed during these meetings. If any literature becomes available which changes the risk/benefit ratio or suggests that conducting the trial is no longer ethical, the IRB will be notified in the form of an Unanticipated Problem submission and the study may be terminated.

HCC #:16-054

Version Date: 008/11/2020

All study data reviewed and discussed during these meetings will be kept confidential. Any breach in subject confidentiality will be reported to the IRB in the form of an Unanticipated Problem submission. The summaries of these meetings are forwarded to the UPCI DSMC which also meets monthly following a designated format.

For all research protocols, there will be a commitment to comply with the IRB's policies for reporting unanticipated problems involving risk to subjects or others (including adverse events). DSMC progress reports, to include a summary of all serious adverse events and modifications, and approval will be submitted to the IRB at the time of renewal.

Protocols with subjects in long-term (survival) follow-up or protocols in data analysis only, will be reviewed twice a year rather than monthly by the disease center DSMB.

Both the UPCI DSMC as well as the individual disease center DSMB have the authority to suspend accrual or further investigate treatment on any trial based on information discussed at these meetings.

All records related to this research study will be stored in a locked environment. Only the researchers affiliated with the research study and their staff will have access to the research records.

13.2 Quality Control and Quality Assurance

Independent monitoring of the clinical study for protocol and Guidelines on Good Clinical Practice compliance will be conducted periodically (i.e., at a minimum of annually) by qualified staff of the Education and Compliance Office – Human Subject Research, Research Conduct and Compliance Office, University of Pittsburgh.

The Investigator (i.e., the study site principal investigator) and the University of Pittsburgh and University of Pittsburgh Medical Center will permit direct access of the study monitors and appropriate regulatory authorities to the study data and to the corresponding source data and documents to verify the accuracy of this data.

13.3 Data Handling and Record-Keeping

The Investigator (i.e., the study site principal investigator) will maintain records in accordance with Good Clinical Practice.

The investigator will retain the specified records and reports for up to 2 years after the marketing application is approved for the investigational drug; or, if a marketing application is not submitted or approved for the investigational drug, until 2 years after investigations under the IND have been discontinued and the FDA so notified.

13.4 Institutional Review Board (IRB) Approval

The investigator (i.e., the study site principal investigator) will obtain, from the University of

HCC #:16-054

Version Date: 008/11/2020

Pittsburgh Institutional Review Board (IRB), prospective approval of the clinical protocol and corresponding informed consent form(s); modifications to the clinical protocol and corresponding informed consent forms, and advertisements (i.e., directed at potential research subjects) for study recruitment, if applicable.

The only circumstance in which a deviation from the current IRB-approved clinical protocol/consent form(s) may be initiated in the absence of prospective IRB approval is to eliminate an apparent immediate hazard to the research subject(s). In such circumstances, the investigator will promptly notify the University of Pittsburgh IRB of the deviation.

The University of Pittsburgh IRB operates in compliance with FDA regulations at [21 CFR Parts 50](#) and [21 CFR 56](#), and in conformance with applicable International Conference on Harmonization (ICH) Guidelines on Good Clinical Practice.

In the event that the University of Pittsburgh IRB requires, as a condition of approval, substantial changes to a clinical protocol submitted under an FDA-accepted IND application, or in the event of an sponsor's decision to modify the previously accepted clinical protocol, the sponsor will submit (i.e., in advance of implementing the change) a Protocol Amendment to the IND describing any change that significantly affects the safety of subjects, the scope of the investigation, or the scientific quality of the study. Examples of protocol changes requiring the submission of a Protocol Amendment include:

- Any increase in drug dosage or duration of exposure of individual subjects to the investigational drug beyond that described in the current protocol, or any significant increase in the number of subjects under study.
- Any significant change in the design of the protocol (such as the addition or deletion of a control group).
- The addition of a new test or procedure that is intended to improve monitoring for, or reduce the risk of, a side effect or AE; or the dropping of a test intended to monitor the safety of the investigational drug.

13.5 Ethical and Scientific Conduct of the Clinical Study

The clinical study will be conducted in accordance with the current IRB-approved clinical protocol; ICH Guidelines on Guidelines on Good Clinical Practice; and relevant policies, requirements, and regulations of the University of Pittsburgh IRB, University of Pittsburgh and University of Pittsburgh Medical Center, Commonwealth of Pennsylvania, and applicable federal agencies.

13.6 Informed Consent

The investigator (i.e., the study site principal investigator) will make certain that an appropriate informed consent process is in place to ensure that potential research subjects, or their authorized representatives, are fully informed about the nature and objectives of the clinical study, the potential risks and benefits of study participation, and their rights as research subjects. The investigator, or a sub-investigator(s) designated by the sponsor, will obtain the written, signed

HCC #:16-054

Version Date: 008/11/2020

informed consent of each subject, or the subject's authorized representative, prior to performing any study-specific procedures on the subject. The date and time that the subject, or the subject's authorized representative, signs the informed consent form and a narrative of the issues discussed during the informed consent process will be documented in the subject's case history. The investigator or sub-investigator will retain the original copy of the signed informed consent form, and a copy will be provided to the subject, or to the subject's authorized representative.

The investigator will make certain that appropriate processes and procedures are in place to ensure that ongoing questions and concerns of enrolled subjects are adequately addressed and that the subjects are informed of any new information that may affect their decision to continue participation in the clinical study. In the event of substantial changes to the clinical study or the risk-to-benefit ratio of study participation, the investigator will obtain the informed consent of enrolled subjects for continued participation in the clinical study. When a reconsent is required, the lead study coordinator will notify all sub-investigators and study coordinators via email that a reconsent is needed. The email notification will also list the changes in the new consent and specify which patients need to be reconsented.

14. STATISTICAL CONSIDERATIONS

14.1 Rationale for study design and sample size

Although platinum-based doublet chemotherapy demonstrates a survival advantage over single agent therapy with pemetrexed, paclitaxel or erlotinib in the 1st line treatment of advanced NSCLC with ECOG PS2 (Lilenbaum et al. 2005; Lilenbaum et al. 2008; Zukin et al. 2013), it has not been universally adopted due to the perceived burden of excess toxicity associated with therapy (West 2013). Our study investigates a possible therapy to address the unmet need of an effective, tolerable first-line therapy for the large population of advanced NSCLC patients with PS2. Durvalumab is in the class of PD-L1 monoclonal antibodies that have yielded durable responses in a sizeable minority of patients, without the side effects of a platinum doublet. A single-arm trial is appropriate given the development stage of durvalumab and the incremental steps required toward staging a much larger trial, such as to assess noninferiority with a platinum-based doublet. The trials cited above in this patient population establish benchmarks for reasonable and unreasonable efficacy and toxicity.

Prior phase II/III clinical trials have demonstrated a median OS of about 5 months with single agent therapy in PS2 patients with advanced NSCLC (Lilenbaum et al. 2005; Lilenbaum et al. 2008; Zukin et al. 2013). A median OS of 9 months with durvalumab (approximately the level achieved by the platinum-based doublets in these trials) would demonstrate a clinically meaningful improvement over the historical control median OS of 5 months with single agent therapy. Assuming 18 months of accrual with 6 months of follow-up, N=50 patients are required to have 85% power for a 90% confidence interval for median survival to exclude 5 months (and 78% power for a 95% confidence interval).

14.2 Analysis cohorts

The safety cohort includes all patients who receive at least one dose of study drug. (SAEs

HCC #:16-054

Version Date: 008/11/2020

occurring following written informed consent but before initiating study therapy will be reported as described in Section 8.3.2, but will not be part of study summaries.)

The primary efficacy cohort may exclude patients who withdraw from study therapy prior to the second cycle for reasons unrelated to disease progression or toxicity. Examples include patients who withdraw due to concerns about insurance coverage, or reluctance to travel an additional distance for study participation. However, these patients will be followed for overall survival if they do not withdraw consent, and will be included in a sensitivity analysis of efficacy endpoints for the full safety cohort.

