14.3 Analysis plan

Summary tables describing the patient cohort will be compiled, including:

- Demographics (age, sex, race, ethnicity, smoking history, recent weight loss)
- Disease history (current stage, tumor sites, histology)
- Comorbidities at start of therapy (cardiac, pulmonary, other)
- PD-L1 expression status

Analysis of primary endpoints:

- The OS curve, median OS, and a 90% confidence interval for the median OS will be estimated by standard methods (the Kaplan-Meier method for survival, and the Greenwood variance formula applied to log-transformed survival) in the efficacy cohort (primary analysis) and safety cohort (sensitivity analysis). Durvalumab will be considered a promising therapy in this population if the estimated median OS is 9 months or greater, and/or the lower bound of a 90% confidence interval for the median OS is greater than 5 months. However, these results will be interpreted in the context of safety data and the presence of durable responses attributed to study therapy.).
- All adverse events that are determined to be possibly, probably or definitely related to treatment will be tabulated according to grade and type, in order of frequency in the safety cohort. Each adverse event will be counted only once per patient, with the highest grade recorded. Serious adverse events and adverse events of special interest (ASEI, defined in section 8.1.3) will also be tabulated by frequency. Listings will be provided for all on-study deaths and adverse events that lead to withdrawal from study.

Lilenbaum et al (2008) observed a rate of grade ≥ 3 adverse events of 41% (90% CI 31%-53%) for a platinum-based doublet, and 27% (90% CI 18%-38%) for erlotinib. In this context of balancing expected toxicity and efficacy, a rate of grade ≥ 3 treatment related adverse events of 30% or less would be acceptable, especially if associated with efficacy in individuals. In a cohort of n=50, a 30% rate of grade ≥ 3 adverse events would have a 90% CI of (21%-41%), demonstrating it is likely more tolerable than the platinum doublet.

Secondary Objectives:

HCC #:16-054

Version Date: 008/11/2020

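### The primary OS analysis may leave out treated patients on the basis of a post-treatment reason; all treated patients should be the primary population

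*Combined protocol and SAP*

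**What the plan says.** Section 14.2 defines a safety cohort of everyone who receives at least one dose. It then says: "The primary efficacy cohort may exclude patients who withdraw from study therapy prior to the second cycle for reasons unrelated to disease progression or toxicity". The reasons are illustrated but not listed in full: "Examples include patients who withdraw due to concerns about insurance coverage, or reluctance to travel an additional distance for study participation". The section adds that "these patients will be followed for overall survival if they do not withdraw consent", and that they "will be included in a sensitivity analysis of efficacy endpoints for the full safety cohort".

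Section 14.3 assigns the roles. OS is estimated "in the efficacy cohort (primary analysis) and safety cohort (sensitivity analysis"). The next sentence is the decision rule: "Durvalumab will be considered a promising therapy in this population if the estimated median OS is 9 months or greater", and/or the lower 90% limit for the median is above 5 months. That sentence names no cohort. Because it directly follows the statement of which analysis is primary, the natural reading is that the restricted cohort drives it. Section 14.3 then adds a qualification: "However, these results will be interpreted in the context of safety data and the presence of durable responses attributed to study therapy".

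Four other places bear on the point:

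- Section 6.6 requires the reason and date of stopping therapy in the case report form.
- Section 6.4 ends all study observation once consent is withdrawn.
- Section 12.1.4.3 has a reporting category for global deterioration without objective progression.
- Section 3.1 requires a life expectancy above 12 weeks.

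Section 14.2 refers to none of these when it defines the exclusion.

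**The concern.** Whether a treated patient counts in the primary analysis depends on something that happens after treatment starts and on how its cause is classified. The plan does not say who classifies, when, whether survival is known by then, or how mixed reasons are handled.

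The classification is also made early. A cycle is 28 days (section 6.1) and the first scheduled on-treatment scan is at week 8 (section 11), so a withdrawal before cycle 2 precedes any scheduled on-treatment scan. All patients have performance status 2. A stated reluctance to travel could partly reflect decline; this is an inference, not something the documents report.

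There is no control arm in which the same exclusion could offset the effect. If the excluded patients do worse than average, the median OS and its lower limit rise against the 5-month benchmark, and an inactive treatment is more likely to be called promising. If the two analyses disagree, the primary label stays with the restricted cohort.

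**Working it through.** **Inputs from the plan.** N = 50, 18 months of accrual, 6 months of follow-up, benchmark 5 months, target 9 months (section 14.1). Kaplan-Meier with Greenwood variance on log survival, and a 90% interval, so z = 1.645 (section 14.3).

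**Reduction to a binomial rule.** Every patient has at least 6 months of follow-up, so without dropout nobody is censored before month 5. The lower limit for the median exceeds 5 months when the lower limit for S(5) exceeds 0.5. With d of n alive at 5 months and S = d/n, this is

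S × exp(−1.645 × √((1 − S)/(nS))) > 0.5.

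For n = 50, d = 30 gives 0.496 and d = 31 gives 0.517, so 31 survivors are needed.

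**The plan's own figure.** Section 14.1 says "N=50 patients are required to have 85% power for a 90% confidence interval for median survival to exclude 5 months". At a 9-month exponential median, S(5) = 0.5^(5/9) = 0.680, and P(at least 31 of 50) = 85.7%. With a 95% interval the cutoff is 32 and the power is 78.0%, against the stated 78%. Both figures reproduce with all 50 patients analysed. At a true median of 5 months, S(5) = 0.50, and P(at least 31 of 50) = 5.9%.

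**Uninformative exclusion.** With S(5) = 0.50 in those kept:

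| n analysed | 49 | 48 | 47 | 46 | 45 | 44 | 43 |
|---|---|---|---|---|---|---|---|
| cutoff | 30 | 30 | 29 | 28 | 28 | 27 | 27 |
| chance | 7.6% | 5.6% | 7.2% | 9.2% | 6.8% | 8.7% | 6.3% |

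The range of 5.6% to 9.2% comes from discreteness alone.

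**Informative exclusion (the number x and median m are assumptions).** Excluded patients are alive at withdrawal at t₀ and then have exponential survival with median m. The true median of all 50 is held at 5 months:

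S_ex = 0.5^((5 − t₀)/m); S_kept = (0.5 − e × S_ex)/(1 − e), with e = x/50.

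Worked case, x = 5, m = 2, t₀ = 1: S_ex = 0.5² = 0.25; S_kept = (0.5 − 0.025)/0.9 = 0.528; P(at least 28 of 45) = 13.1%.

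| x | m (months) | t₀ (months) | S_kept(5) | chance | same n, uninformative |
|---|---|---|---|---|---|
| 5 | 5 | 1 | 0.492 | 5.4% | 6.8% |
| 5 | 4 | 1 | 0.500 | 6.8% | 6.8% |
| 5 | 3 | 1 | 0.511 | 9.0% | 6.8% |
| 5 | 2 | 1 | 0.528 | 13.1% | 6.8% |
| 7 | 2 | 1 | 0.541 | 16.0% | 6.3% |
| 1 | 2 | 1 | 0.505 | 8.7% | 7.6% |
| 2 | 2 | 1 | 0.510 | 7.4% | 5.6% |
| 3 | 2 | 1 | 0.516 | 10.7% | 7.2% |
| 5 | 2 | 0.5 | 0.532 | 14.4% | 6.8% |
| 7 | 2 | 0.5 | 0.547 | 18.2% | 6.3% |

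The apparent median, 5 × ln 2 / (−ln S_kept), is 5.4 months for 5 excluded and 5.6 months for 7 excluded at m = 2, t₀ = 1.

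**The 9-month criterion.** In 40,000 simulated trials with the planned accrual, adding the alternative of a median of at least 9 months moves the chance by at most 0.2 points: 5.8% for all 50, 13.1% (restricted cohort, 5 at 2 months) and 16.3% (7 at 2 months).

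**Keeping everyone.** With the 5 patients at m = 2 retained and followed, P(at least 31 of 50) is 5.7%. If some of them also withdraw consent and are censored at month 1, simulation gives:

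| m (months) | 2 of 5 censored | all 5 censored | restricted cohort |
|---|---|---|---|
| 2 | about 11% | about 15% | 13.1% |
| 3 | about 10% | about 11% | 9.0% |

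**The case against.** The plan already contains most of the protection. Withdrawals for progression or toxicity, the plainly informative ones, stay in. Symptomatic deterioration has its own category and is grouped with toxicity for tumor follow-up in Appendix E, so it would be hard to call unrelated. The reason for stopping is a required record, and the all-treated analysis is prespecified. The wording can be read as defining a class of logistical withdrawals, not as licensing case-by-case choice. The decision sentence names no cohort and is tempered by safety and durable responses. Setting aside patients who leave for logistical reasons after one cycle is a defensible phase II question.

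The size is also conditional. At a 4-month median the chance equals that of uninformative exclusion, and at 3 months it lies inside the discreteness range. The excess needs several excluded patients with a 2-month median, which is extreme given the life-expectancy criterion. Consent withdrawal also undercuts the remedy: with a 3-month median, two consent withdrawals out of five are enough to remove the gain.

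All of this limits the weight of the point, and the figures are correct. It does not remove the point. Neither the required record nor the deterioration category is tied to the exclusion rule, the wording is optional, and where the two analyses differ the plan calls the restricted one primary. Being able to see a disagreement is different from having said in advance which result governs.

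**Conclusion.** The concern holds, as a cheap improvement and not as a flaw that invalidates the trial. The primary OS population is a discretionary subset defined after treatment starts. Upward bias is possible but not established: it requires that excluded patients have worse survival than the rest, and the documents give neither their number nor their prognosis. Under the assumptions shown, the chance of a lower limit above 5 months at a true 5-month median moves from 5.9% to between 5.4% and 16.0% for month-1 withdrawal, and up to 18.2% for withdrawal at half a month. Only the cases with several patients at a 2-month median stand clear of discreteness. The stated sample size already corresponds to analysing all 50 patients, so the change does not disturb it. Confidence is medium, because the practical effect depends on how many such withdrawals occur and how many keep their consent.

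**What to change.** In sections 14.2 and 14.3:

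1. Make all patients with at least one dose the primary OS population, and state that the 9-month and 5-month criteria apply to it. Patients without further observation are censored when last known alive.
2. Keep the restricted cohort as the sensitivity analysis. Replace the optional wording with a fixed rule based on the reason recorded in the case report form, applied by a named role without knowledge of survival. The rule should say how mixed reasons and symptomatic deterioration are classed.

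The cost is wording only; both analyses and the survival follow-up are already planned. The headline median may be slightly lower. The change does not recover survival after consent withdrawal. If most early leavers also withdraw consent, it brings no gain on the false-positive chance, and the all-treated figure can be slightly higher than the restricted one. Even then, it removes the discretion from the primary analysis.
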